5.6 Criteria for Removal from Study

Patients will be removed from study for one of the following reasons: completed 30-day followup period, toxicities are unresolved but stabilized, patient enrolls on another protocol, or patient receives other type of treatment-intent therapy. The reason for study removal and the date the patient was removed must be documented in the medical record.

6. DELAYS/DOSE MODIFICATIONS

See below for dose delay and management guidance, indicating when the study agent should be held or discontinued due to specific adverse events.

6.1 Drug-related toxicity

- 6.1.1 If a patient has a DLT during cycle 1, no further treatment will be administered for that cycle and the dose will be reduced by one dose level for the next cycle.
- 6.1.2 If the patient has a DLT during any subsequent cycle, no further treatment will be administered for that cycle and the dose will be reduced by one dose level for the next cycles and the patient will not be eligible for intra-patient dose escalation.
- 6.1.3 If Grade 3 diarrhea occurs (increase of >6 stools/day over baseline) but resolved to ≤ grade 2 with anti-diarrheal within 72 hours, the patient will receive the same dose on subsequent cycles with anti-diarrheal treatment as stated in Section 5.3.2. If Grade ≥3 diarrhea continues > 72 hours despite treatment, this constitutes a DLT (see Section 5.2) and LMP744 will be dose reduced by one dose level for subsequent cycles.

| Diarrhea grade after 72 hours of anti-diarrheal med | Management/Next Dose for LMP744 | |
|---|--|--|
| \leq Grade 1 | No change in dose | |
| Grade 2 | Resume at same dose level. | |
| Grade 3 | Hold [*] until \leq Grade 2. Resume at one dose level lower, if refractory. ^{**} | |
| Grade 4 | | |
| *Patients requiring a delay of >2 weeks will be taken off protocol therapy. | | |
| **Patients requiring > two dose reductions will be taken off protocol therapy. | | |
| Recommended management: Loperamide antidiarrheal therapy | | |
| Dosage schedule: 4 mg at first onset, followed by 2 mg with each loose motion until diarrhea-free for | | |
| 12 hours (maximum dosage: 16 mg/24 hours) | | |
| Adjunct anti-diarrheal therapy is permitted and should be recorded when used. | | |

6.1.4 If Grade ≥2 nausea and vomiting require anti-emetics, the patient will receive antiemetics prior to the administration of subsequent doses of LMP744 as described in Section 5.3.1.

| Nausea grade after 72 hours of antiemetic support | Management/Next Dose for LMP744 | |
|--|---|--|
| \leq Grade 1 | No change in dose | |
| Grade 2 | Resume at same dose level. | |
| Grade 3 | Hold [*] until \leq Grade 2. Resume at one dose level lower if refractory. ^{**} | |
| Grade 4 | Off protocol therapy | |
| * Patients requiring a delay of >2 weeks will be taken off protocol therapy. | | |
| **Patients requiring > two dose reductions will be taken off protocol therapy. | | |
| Recommended management: antiemetics. | | |

| Vomiting grade after 72 hours of antiemetic support | Management/Next Dose for LMP744 | |
|--|---------------------------------|--|
| \leq Grade 1 | No change in dose | |

| Vomiting grade after 72 hours of antiemetic support | Management/Next Dose for LMP744 | |
|--|--|--|
| Grade 2 | Resume at same dose level. | |
| Grade 3 | Hold [*] until \leq Grade 2. Resume at one dose level lower, if refractory. ^{**} | |
| Grade 4 | Off protocol therapy | |
| *Patients requiring a delay of >2 weeks should go off protocol therapy. | | |
| **Patients requiring > two dose reductions should go off protocol therapy. | | |
| Recommended management: antiemetics. | | |

6.1.5 Patients will be allowed to continue treatment for decreased leucocytes, ANC and hemoglobin that recover to a Grade ≤ 2 toxicity and platelets to Grade ≤ 1 . Dose reduction to one dose level lower may also be considered if ≥ 4 occurrences of symptomatic anemia requiring blood transfusion, at the discretion of the clinician.

| Neutropenia | Management/Next Cycle | |
|--|---|--|
| ≤ Grade 1 | No change in dose | |
| Grade 2 | Resume at same dose level. | |
| Grade 3 | Hold [*] until < Grade 2. Resume at same dose level. | |
| Grade 4 | Hold [*] until < Grade 2. Resume at one dose level lower ^{**} | |
| *Patients requiring a delay of >2 weeks will be taken off protocol therapy. | | |
| **Patients requiring > two dose reductions will be taken off protocol therapy. | | |
| Use of growth factors per ASCO guidelines. | | |

| Thrombocytopenia | Management/Next Cycle | |
|--|--|--|
| ≤ Grade 1 | No change in dose | |
| Grade 2 | Hold until \leq Grade 1. Resume at same dose level. | |
| Grade 3 | Hold [*] until < Grade 1. Resume at one dose level lower, if indicated. ^{**} | |
| Grade 4 | Hold [*] until < Grade 1. Resume at one dose level lower. ^{**} | |
| *Patients requiring a delay of >2 weeks will be taken off protocol therapy. | | |
| **Patients requiring > two dose reductions will be taken off protocol therapy. | | |

| Anemia | Management/Next Cycle | |
|--|--|--|
| ≤ Grade 1 | No change in dose | |
| Grade 2 | Resume at same dose level. | |
| Grade 3 | Hold* until < Grade 2. Resume at one dose level lower, if indicated. ** | |
| Grade 4 | Hold [*] until < Grade 2. Resume at one dose level lower. ^{**} | |
| *Patients requiring a delay of >2 weeks should go off protocol therapy. | | |
| **Patients requiring > two dose reductions should go off protocol therapy. | | |

6.1.6 If a patient develops hives or swelling, the patient will receive at minimum diphenhydramine as described in Section 5.3.7. Once the reaction has subsided, patients may be rechallenged with the original dose of LMP744. In case the reaction does not subside within 2 hours or the patient develops a subsequent reaction on rechallenge, the study drug will be discontinued and the patient taken off study. A grade ≤ 2 infusion reaction will not be considered a DLT; pre-medication will be added to treatment on subsequent dosing if patients experience \leq grade 2 infusion reaction.

6.2 Intra-patient Dose Escalation and De-escalation

Intra-patient dose ESCALATION is permitted ONLY if:

- 1. Patients did not experience toxicity >Grade 1 that is possibly, probably, or definitely related to the study drug after one cycle at the initial dose level (subsequent cycles may be delayed up to 14 days past the end of the previous cycle of 28 days to allow for toxicities to resolve).
- 2. Higher doses have been evaluated and completed without a DLT.
- 3. The patient's disease has not progressed.
- 4. There is no concern of cumulative toxicity.

Doses may be escalated by one dose level for every subsequent cycle, provided conditions 1-4 are met, up to the last evaluated dose level NOT associated with DLT.

If a patient experiences DLT during a cycle, the dose will be REDUCED by one level (if there is a lower dose level, see Section 5.1.2) for the next cycle, provided toxicity has recovered to \leq Grade 1 within 14 days after completing a 28-day cycle, and the patient's disease is stable or responding. If a patient is dose reduced twice and still experiences a DLT, then the patient would be removed from the study. If no lower dose level exists, then the patient will be removed from the study.

6.3 Dose and Cycle delays

Subsequent cycles may be delayed up to 14 days past the end of the previous cycle of 28 days for resolution of toxicity. Patients will be allowed up to 2 dose reductions. If more than 2 dose reductions are required, the patient will be removed from the study. For patients on dose level 1, only 1 dose reduction will be allowed (see Section 5.1.2).

6.4 **Reporting and Exclusions**

6.4.1 Evaluation of toxicity: A cycle is defined as being 28 days, with Day 1 starting the first day of the 5-day treatment. All patients who receive a dose of LMP744 will be evaluable for toxicity regardless of whether they complete a cycle. If therapy is delayed, the next cycle day 1 will be the day therapy is administered.

Patients who do not complete a cycle of therapy for reasons other than toxicity will be replaced.

6.4.2 Evaluation of response: All patients included in the study who receive any treatment at all will be assessed for response to treatment, even if there are major protocol treatment deviations or if they are ineligible. All patients who meet the eligibility criteria will be included in the main analysis of the response rate. Secondary analyses may be restricted to patients without major protocol violations.

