5.1.2 Dose Escalation Cohorts

During the accelerated phase, there will be one patient per dose level. The patient will be assessed for dose-limiting toxicity (DLT) and grade 2 toxicity (both parameters defined in Section 5.2) during cycle 1 of treatment.

The accelerated phase of dose-escalation will end, and change to a standard 3+3 design, when:

- one patient experiences DLT during cycle 1, OR
- at the first instance of grade 2 drug-associated toxicity, when two additional patients will be enrolled. If two different patients experience Grade 2 toxicity during cycle 1, the escalation plan will end.

As of Amendment G (10/18/18), a patient on Dose Level 6 experienced DLT during cycle 1, and the study reverted to a standard 3+3 design.

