11.2.1 Definitions

Evaluable for toxicity: All patients will be evaluable for toxicity from the time of their first treatment with LMP744.

Evaluable for objective response: Only those patients who have measurable disease present at baseline, have received at least one cycle of therapy, and have had their disease re-evaluated will be considered evaluable for response. These patients will have their response classified according to the definitions stated below. (Note: Patients who exhibit objective disease progression prior to the end of cycle 1 will also be considered evaluable.)

Evaluable Non-Target Disease Response: Patients who have lesions present at baseline that are evaluable but do not meet the definitions of measurable disease, have received at least one cycle of therapy, and have had their disease re-evaluated will be considered evaluable for non-target disease. The response assessment is based on the presence, absence, or unequivocal progression of the lesions.

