13. STATISTICAL CONSIDERATIONS

13.1 Study Design/Endpoints

The primary objective of this trial is to establish the safety, tolerability, and MTD of LMP744 administered intravenously daily for 5 days in 28-day cycles, to patients with refractory solid tumors. This study will follow design 3 of the Simon accelerated titration designs (26), with dose escalation proceeding in 1-patient cohorts and switching to standard 3+3 dose escalation of dose levels when specific criteria are met (Section 5.1.1). (*Note: As of Amendment G* [10/18/18], the study switched to standard 3+3 dose escalation. As of Amendment I [9/25/19], there is flexibility to accrue up to an additional 3 patients on any dose level that has 1 DLT observed among 6 patients [see Section 5.1.2.1]. As of Amendment L [date 6/7/2021], the MTD has been identified and the expansion cohort will begin accrual [see Section 5.1.2.2].)

Following this, another 15 patients will be treated at the MTD on an expansion cohort, which will include mandatory biopsies. With 15 patients and a tumor biopsy QA criteria failure rate of 50% with respect to paired (pre- and post-dose) biopsies, we have an 85% likelihood of having at least 6 usable PD samples, and 95% likelihood of having at least 5 usable samples from the expansion cohort. Biopsy tissue quality will be monitored and accrual to the expansion phase will stop once we have obtained 6 usable paired samples. With 6 PD sample pairs, there is 90% power to detect a treatment effect equivalent to 1.85 SD's (associated with the intra-patient baseline variability of the PD marker) with the paired 2-sample T-test, at the 1-sided .05 significance level, for a given PD variable of interest. PD variables may be log-transformed to achieve more nearly normal distributions.

DLTs will be summarized descriptively according to dose level. In addition, the relation of dose level with presence or absence of DLT will be analyzed using logistic regression, as described by Simon (20).

All AEs will be tabulated by type and grade according to dose level. In addition, the presence or absence of grade 2 or higher toxicity for each patient in each treatment cycle will be modeled using random effects logistic regression as described by Simon (20), incorporating dose during the cycle and total dose for previous cycles, with intra-patient random effects.

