13.2 Sample Size/Accrual Rate

As of Amendment G (10/18/18), if all dose levels are evaluated, we anticipate enrolling a minimum of 35 patients and a maximum of 47 patients. In order to allow for a small number of patients who may not be evaluable, the accrual ceiling for this trial is set at 53 patients.

It is anticipated that 1 patient may be enrolled per month onto this study during the accelerated titration stage (already completed) and 1-2 patients/month thereafter. It is expected that 25-35 months will be required to accrue the number of patients necessary to complete the trial.

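### Does leaving the DLT denominator unnamed in section 13.1 put the dose-level DLT report at risk?

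*Combined protocol and SAP*

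**What the plan says.** Section 6.4.1 defines who is assessed for toxicity: "All patients who receive a dose of LMP744 will be evaluable for toxicity regardless of whether they complete a cycle". Section 11.2.1 agrees: "All patients will be evaluable for toxicity from the time of their first treatment with LMP744". Section 6.4.1 then adds a replacement rule: "Patients who do not complete a cycle of therapy for reasons other than toxicity will be replaced". It does not say whether a replaced patient leaves any analysis.

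Section 13.1 plans two DLT analyses. The first is a table: "DLTs will be summarized descriptively according to dose level". The second is a model: "the relation of dose level with presence or absence of DLT will be analyzed using logistic regression". Neither sentence names an analysis set, and neither says whether the 15 expansion patients, who are treated at the MTD, are included.

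Section 13.2 gives the enrolment figures: "we anticipate enrolling a minimum of 35 patients and a maximum of 47 patients". It then leaves room for a small number of "patients who may not be evaluable, the accrual ceiling for this trial is set at 53 patients". It does not say what they might not be evaluable for.

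Section 5.1.2.1 bases escalation on cycle 1 DLTs among 3 or 6 patients, with up to 3 more at the investigator's discretion. Section 5.1.2 records that "a patient on Dose Level 6 experienced DLT during cycle 1". Section 5.1.2.2 records that dose level 6 was identified as the MTD at Amendment L.

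**The concern.** Safety and the MTD are the primary objective, and the DLT rate at each dose level is how the result will be reported. A patient who leaves during cycle 1 for a reason unrelated to toxicity has not been observed for the full DLT window. Counting that patient as free of DLT pulls the rate down; leaving the patient out does not. The plan contains wording for both: all dosed patients are evaluable for toxicity, yet some are replaced. In cohorts of 3 to 9 patients, one person visibly changes a percentage.

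A second, smaller point is that the replacement rule turns on toxicity rather than on DLT. Under sections 5.3.7 and 6.1.6 a patient can be taken off study for a reaction of grade 2 or lower, which those sections do not count as a DLT. On a literal reading that patient is not replaced, and may be counted as having completed without a DLT.

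At worst, two analysts working from the same data would print different DLT rates and different regression fits for the primary objective.

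**Working it through.** **Are the statements compatible?** They answer three separate questions.

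| Question | Where answered | Answer |
|---|---|---|
| Whose toxicities are recorded and tabulated? | 6.4.1, 11.2.1 | Every dosed patient |
| Who is replaced? | 6.4.1 | Non-completers for reasons other than toxicity |
| Who enters the DLT table and regression? | 13.1 | Not stated |

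The first two can both hold: a patient can be in the adverse event tables and still be replaced for the cohort decision. Only the third is open, so this is an omission and not a contradiction.

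**The plan's own figure.** The ceiling is the maximum plus an allowance: 53 − 47 = 6, or 6/53 = 11.3%. No non-evaluable rate is stated, so the allowance cannot be derived formally. Assumed rates of 10% and 11% both give 53 (47/0.90 = 52.2; 47/0.89 = 52.8), and 12% gives 54 (47/0.88 = 53.4). The allowance need not concern DLTs, since the plan also has response evaluability (11.2.1) and usable biopsy pairs (13.1).

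**Why replacement matters for escalation.** With true DLT rate p, the basic 3+3 rule escalates with probability (1 − p)³ + 3p(1 − p)⁵. At p = 0.30 this is 0.343 + 0.151 = 0.494. Suppose non-completers filled slots as non-DLTs, at an assumed share of 6/53. The effective rate would be 0.30 × 47/53 = 0.266, and the probability 0.395 + 0.170 = 0.565. The replacement rule in 6.4.1 is there to prevent that shift, and escalation is now complete.

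**Effect on the reported rate at dose level 6.** The documents give no final count. One cycle 1 DLT at that level and its selection as the MTD fit 1 in 6, which is assumed here. Intervals are exact 95%.

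| Replaced non-DLT patients counted | Rate | Interval |
|---|---|---|
| 0 | 1/6 = 16.7% | 0.4% to 64.1% |
| 1 | 1/7 = 14.3% | 0.4% to 57.9% |
| 2 | 1/8 = 12.5% | 0.3% to 52.7% |
| 3 | 1/9 = 11.1% | 0.3% to 48.2% |

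Section 5.1.2.1 also allows 9 patients at a level. From 1/9 = 11.1%, one replaced patient gives 1/10 = 10.0%. With the 15 expansion patients and an assumed 3 DLTs in 6 + 15 = 21, the rate is 14.3%; three replaced patients would make it 3/24 = 12.5%.

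**Effect on the regression.** Logistic regression on log dose, by maximum likelihood, assuming 0/1 at levels 1 to 5, 1/6 at level 6, and each of four outcomes at level 7 (260 mg/m²/day):

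| Assumed level 7 | Fitted at level 6: none / one / two replaced there | Fitted at level 7: none / one replaced there |
|---|---|---|
| 2/3 | 16.6% / 14.3% / 12.5% | 66.8% / 50.3% |
| 3/6 | 16.4% / 14.1% / 12.4% | 50.2% / 43.2% |
| 2/6 | 15.5% / 13.7% / 12.1% | 34.2% / 29.7% |
| 2/9 | 13.7% / 12.5% / 11.4% | 23.7% / 21.6% |

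The unknown outcome at level 7 moves its fitted rate between 23.7% and 66.8%. One replaced patient moves it by 2 to 17 percentage points. In the four scenarios with nobody replaced, the dose slope is between 0.7 and 1.4 standard errors from zero, so the fit is weak whichever set is used.

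**The case for a change.** The best case for acting is that these are the primary analyses and no section defines a DLT-evaluable patient, although section 6.4.2 does name the set for the response rate, which is exploratory. In small cohorts the denominator is visible to every reader, and one added sentence would remove the discretion. All of that is accurate. An optional sentence in 13.1 would do no harm, and naming the denominator in the report achieves the same end.

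It falls short of requiring a change for four reasons. First, the text already leans towards workable answers. DLTs are graded toxicities, so 6.4.1 offers all dosed patients as a literal default for the table, while the cohort decisions supply the set without replaced patients. Expansion patients are at dose level 6, and a summary by dose level excludes nobody. Second, section 13.1 refers the regression to a published method (the reference number appears to point to the wrong list entry), so the text here is not necessarily the whole specification. Third, every count in the illustrations is assumed, and the documents record no replaced or early-stopped patient. Fourth, the reaction route in sections 5.3.7 and 6.1.6 is narrow: it needs a grade 2 or lower reaction that lasts beyond 2 hours or recurs on rechallenge, and the October 2021 adverse event list in section 7.1.1 names no allergic or infusion reaction.

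**Conclusion.** The gap is real but is missing detail that an analyst fills in the ordinary way: adverse events in all treated patients, DLT rates with the denominator printed, and replaced and expansion patients accounted for in the text or a footnote. No stated rule gives a wrong result. The MTD was settled at Amendment L, and no DLT rule is set for the expansion cohort, so no dosing decision turns on the choice.

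The effect is zero if no dosed patient was replaced and the report states how expansion patients are counted. Otherwise, on an assumed 1 in 6 at dose level 6, one to three replaced patients lower the raw rate from 16.7% to between 14.3% and 11.1%, well inside an interval of 0.4% to 64.1%. At level 7 a single patient can matter more if that cohort had only 3 patients (66.8% to 50.3% fitted), but that is one assumed outcome on a very imprecise fit. The conclusion would need another look only if the records showed several cycle 1 replacements concentrated at one dose level.

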5.1.2.1 Standard 3+3 Dose Escalation Phase

In the standard phase of the dose escalation, 3 patients will be treated at the final accelerated dose level and initially at each new dose level. Dose escalation will be based on DLTs observed during the first cycle of treatment. If none of the 3 patients develop DLT at the dose administered, escalation will continue in cohorts of 3 patients each. If a DLT during the first cycle is observed in any of the 3 patients, then the cohort will expand to 6 patients. If a second DLT is observed during cycle 1, then up to a total of 6 patients will be enrolled to the next lower cohort. If no more than 1 in 6 patients in a dose level have DLT during the first cycle, dose escalation is permitted.

At the PI's discretion, up to an additional 3 patients may be accrued at a dose level with 1 DLT observed among the 6 patients or no DLTs observed among the first 3 patients, to further assess safety. Dose escalation will proceed if no additional DLTs are observed. If 1 additional DLT is observed, the prior dose will be declared the MTD, once 6 patients have been treated with no more than 1 DLT observed.

| Number of Patients with DLT at a Given Dose Level | Escalation Decision Rule |
|--|---|
| 0 out of 3 | Enter 3 patients at the next dose level. |
| ≥2 | Dose escalation will be stopped. This dose level will be declared the maximally administered dose (highest dose administered). Three (3) additional patients will be entered at the next lowest dose level if only 3 patients were treated previously at that dose. |
| 1 out of 3 | Enter at least 3 more patients at this dose level. If 0 of these 3 patients experience DLT, proceed to the next dose level. If 1 or more of this group suffer DLT, then dose escalation is stopped, |

DLTs seen after the first cycle will not affect the dose escalation decisions.

| | and this dose is declared the maximally administered dose. Three (3) additional patients will be entered at the next lowest dose level if only 3 patients were treated previously at that dose. | |
|---|---|--|
| ≤1 out of 6 at highest dose level below the maximally administered dose | This is generally the recommended phase 2 dose. At least 6 patients must be entered at the recommended phase 2 dose. | |

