5.2 Definition of Dose-Limiting Toxicity

- 5.2.1 Grade \geq 3 non-hematologic toxicity will be considered dose limiting, with the following exceptions:
 - 5.2.1.1 Grade 3 fatigue lasting \leq 7 days.

5.2.1.2 Grade 3 diarrhea will only be considered dose limiting if, after 48 hours, it is refractory to treatment as outlined in Section 5.3.2. Grade 4 diarrhea will be dose limiting.

5.2.1.3 Grade 3 nausea and vomiting will be considered dose limiting after 48 hours if it is refractory to maximal anti-emetic therapy and unable to be corrected to Grade 1 or baseline. Grade 2 nausea or vomiting after 72 hours despite three anti-emetogenic agents will also be considered dose limiting.

5.2.1.4 Grade 3 rise in creatinine, not corrected to Grade 1 or baseline after intravenous fluids within 24 hours, will be considered dose limiting. All Grade 4 rises in creatinine will be dose limiting.

5.2.1.5 Grade 3 electrolyte toxicities unable to be corrected to Grade 2 or baseline within 24 hours will be considered dose limiting.

5.2.2 Grade 4 hematological toxicity will be considered dose limiting if it meets the criteria below. Lymphopenia (any grade) will not be considered dose limiting for all

subjects.

- 5.2.2.1 Neutropenia: Grade 4 neutropenia for >5 days without fever or infection will be considered dose limiting. Grade 4 neutropenia of any duration accompanied by fever or infection will be considered dose limiting. Twice weekly blood draws will be needed (after onset of grade 4 neutropenia) to monitor duration of neutropenia for the first 2 cycles. On subsequent cycles (cycle 3 and beyond), weekly blood draws will be monitored at the onset of grade 4 neutropenia.
- 5.2.2.2 Thrombocytopenia: Grade 4 thrombocytopenia will be considered dose limiting. Grade 3 thrombocytopenia associated with bleeding will be considered dose limiting.
- 5.2.2.3 Anemia: Grade 4 anemia will be considered dose limiting.
- 5.2.3 Any neurotoxicity Grade ≥ 2 that is not reversible to a Grade ≤ 1 within 2 weeks will be considered dose limiting.
- 5.2.4 Any non-hematologic Grade 2 toxicity that does not resolve to Grade ≤1 or baseline within 14 days despite adequate treatment as described in Section 5.3 will be considered dose limiting, except for alopecia.

Management and dose modifications associated with the above adverse events are outlined in Section 6.

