5.3.7 Allergic Reaction

If a patient develops hives or swelling, the LMP744 infusion will be held and at a minimum diphenhydramine administered at a dose of 50 mg IV. Other medications (such as steroids or epinephrine) can be used at the discretion of the clinician. Once the reaction has subsided, patients may be rechallenged with the original dose of LMP744. In case the reaction does not subside within 2 hours or the patient develops a subsequent reaction on rechallenge, the study drug will be discontinued and the patient taken off study. A grade ≤ 2 allergic reaction will not be considered a DLT; pre-medication will be added to treatment on subsequent dosing if patients experience \leq grade 2 infusion

reaction.

- 5.3.8 Inhibitors and Inducers of ABCG2 and P-gp LMP744 is a substrate for ATP-binding cassette transporter protein ABCG2 and P-gp. Unless medically necessary, avoid the use of strong inhibitors and inducers of these transporters.
- 5.3.9 Cytochromes P450 Inhibitors and Inducers, and Inhibitors of Drug Transporters The pathways by which LMP744 is eliminated are not known. Unless medically necessary, avoid the use of strong inhibitors and inducers of all major drug metabolizing enzymes and drug transporters.

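### Section 6.4.1 does not replace patients stopped in cycle 1 for toxicity that is not a DLT, so they fill a 3+3 place as DLT-free without the planned five doses

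*Combined protocol and SAP*

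**What the plan says.** Four rules meet here.

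- **Evaluability and replacement (Section 6.4.1).** "All patients who receive a dose of LMP744 will be evaluable for toxicity regardless of whether they complete a cycle". On replacement: "Patients who do not complete a cycle of therapy for reasons other than toxicity will be replaced". A cycle is defined there as 28 days.
- **Escalation (Section 5.1.2.1).** "Dose escalation will be based on DLTs observed during the first cycle of treatment", and "If none of the 3 patients develop DLT at the dose administered, escalation will continue" in further cohorts of three. The MTD requires no more than 1 DLT in 6 patients. No minimum exposure is set and no DLT-evaluable population is defined. Section 13.2 allows for a few patients who may not be evaluable but does not say who they are.
- **Allergic or infusion reaction (Sections 5.3.7 and 6.1.6).** If hives or swelling do not subside within 2 hours, or return on rechallenge, "the study drug will be discontinued and the patient taken off study". For Grade 2 or lower, the "allergic reaction will not be considered a DLT"; Section 6.1.6 says the same of an infusion reaction.
- **DLT definition (Section 5.2).** No criterion covers missed doses or stopping treatment for toxicity. Section 5.2.4 catches a Grade 2 non-hematologic toxicity only if it is still unresolved at 14 days.

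**The concern.** Not replacing patients who stop for toxicity is sound when every such stop is itself a DLT: the patient has supplied the event and the place is properly used. Sections 5.3.7 and 6.1.6 break that link by creating a toxicity stop that is, by rule, not an event. The patient then holds a place in the denominator, adds nothing to the numerator, and may have received only part of the first infusion.

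The primary objective is safety, tolerability and the MTD of five daily doses. A denominator that includes patients who did not receive the five doses makes a dose look better tolerated on that schedule than the data show. The same denominators feed the DLT summary and the dose-DLT logistic regression in Section 13.1.

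The situation is foreseeable. Section 2.3 reports allergic reactions in dogs in all the pilot dog studies and facial swelling at the top dose of the definitive study, and Section 5.1 requires monitoring for reactions in cycle 1.

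**Working it through.** The documents give no operating characteristics for the 3+3 rule, so there is no stated figure to reproduce first.

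**Step 1. Trace one patient.** Take Grade 2 hives at the first infusion that recur on rechallenge.

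1. Sections 5.3.7 and 6.1.6: drug stopped, patient off study.
2. The same sections: not a DLT. If the hives clear within 14 days, Section 5.2.4 does not make them one.
3. Section 6.4.1: one dose is enough to be evaluable for toxicity. The cycle was not completed because of toxicity, so there is no replacement.
4. Section 5.1.2.1: no cycle-1 DLT, so the patient counts on the DLT-free side of 0/3, 1/3 or 1/6.

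Item 4 is an inference from reading two sections together; no single sentence states it.

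**Step 2. Effect if one such patient is among the first three.** Let p be the assumed cycle-1 DLT risk of a fully treated patient and q = 1 − p. A level passes with 0/3, or with 1/3 followed by 0/3.

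- Three fully treated patients: q³ + 3pq²·q³
- One of the three with no residual DLT risk: q² + 2pq·q³

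At p = 0.40: 0.216 + 0.093 = 0.309, against 0.360 + 0.104 = 0.464.

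| Assumed p | Three fully treated | One of three cannot show a DLT |
|---|---|---|
| 33% | 43.4% | 58.2% |
| 40% | 30.9% | 46.4% |
| 50% | 17.2% | 31.2% |

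For the rule of at most 1 DLT in 6 at p = 0.40: with six fully treated patients 0.6⁶ + 6(0.4)(0.6⁵) = 0.233; with five plus one such patient 0.6⁵ + 5(0.4)(0.6⁴) = 0.337.

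**Step 3. Average over how often it happens.** Let d be the chance that an enrolled patient has a cycle-1 DLT and w the chance of being stopped in cycle 1 for toxicity that is not a DLT. Neither is in the documents; the ranges are assumptions. As written, the per-patient event rate is d. With replacement it is d/(1 − w). Each goes into q³ + 3pq⁵.

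At d = 0.20, w = 0.10: as written, 0.512 + 0.197 = 0.709. With replacement p = 0.20/0.90 = 0.222, giving 0.471 + 0.190 = 0.660.

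| d | w | As written | With replacement |
|---|---|---|---|
| 10% | 10% | 90.6% | 88.7% |
| 20% | 5% | 70.9% | 68.6% |
| 20% | 10% | 70.9% | 66.0% |
| 20% | 20% | 70.9% | 60.0% |
| 25% | 10% | 60.0% | 54.0% |

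The 1-in-6 rule at d = 20%, w = 10% gives 65.5% against 60.1%.

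**Step 4. Join the two.** Keep the 40% risk of Step 2 for fully treated patients and let w = 10%. As written the event rate is 0.40 × 0.90 = 0.36, and the pass probability is 0.64³ + 3(0.36)(0.64⁵) = 0.262 + 0.116 = 0.378, against 0.309 with replacement. Averaging reduces the 15-point conditional shift to about 7 points.

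**The case against.** Several points on the other side are fair.

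- **Frequency.** The list of events possibly related to LMP744 in Section 7.1.1, dated October 2021 and so later than the MTD declaration, contains no allergic, hypersensitivity or infusion reaction. These appear only under animal data. No document reports a patient stopped this way. This stands, and it is why the averaged figures are the better guide to expected size.
- **Zero residual risk.** Step 2 assumes the stopped patient cannot have a DLT. A Grade 3 or higher reaction on rechallenge would come under Section 5.2.1, and a partial dose carries some risk. So 46% is an upper bound.
- **Other safeguards.** Section 5.1.2.1 allows up to 3 extra patients at a level with 0/3 or 1/6 DLTs. Section 13.1 tabulates all adverse events and models Grade 2 or higher toxicity by cycle. Section 12.2 provides weekly case review and a safety committee. These expose the event, but the extra patients are discretionary and none of this changes who counts in the DLT denominator.
- **Timing.** With Amendment L the MTD was declared as 190 mg/m²/day. The expansion cohort has no stated DLT decision rule, so a new replacement rule changes no escalation decision already taken. What remains is the denominators and the reported MTD result.

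Two stronger readings are tempting.

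A reader might infer that hematologic delays fall into the same gap. Section 6.1.5 says "Patients requiring a delay of >2 weeks will be taken off protocol therapy", while Section 5.2.2 leaves some of the toxicities behind such delays outside the DLT definition; for example, "Grade 3 thrombocytopenia associated with bleeding will be considered dose limiting", but not without bleeding. The documents do not support that reading. A patient whose second cycle is delayed that long has normally finished the 28 days of cycle 1 and been observed for the whole DLT window. The replacement sentence does not govern that patient, and whether a delay should be dose limiting is a matter for the DLT definition.

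A reader might also infer that a patient stopped on day 1 goes unobserved. Section 5.5 provides 30 days of follow-up after the last dose with a call on Days 27–30, unless other treatment, another protocol or death comes first. The defensible statement is that the five doses were not given.

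**Conclusion.** The point holds for patients stopped in cycle 1 by a Grade 2 or lower allergic or infusion reaction. They are neither events nor replaced, and the DLT rate is biased downward. The direction follows from the rules alone.

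The size rests on two rates the documents do not give. Over the assumed ranges in Step 3, replacement lowers the chance of passing a level by about 2 to 11 points, and by 4.9 points at 20% DLT risk and 10% frequency. The shift of about 15 points applies only when such a patient is known to be among the first three and has no remaining DLT risk.

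This does not show that 190 mg/m²/day was wrongly declared: nothing says such a patient was enrolled at that or any other level. Nor does it show that these reactions ought to be DLTs; the protocol expressly decides otherwise, and that choice belongs to the sponsor.

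**What to change.** 1. **Section 6.4.1.** For the DLT and MTD decision, replace any patient who does not complete cycle 1 for a reason other than a DLT. Define the DLT-evaluable set accordingly, and keep these patients in every safety table.
2. **Section 13.1.** Base the DLT summary and the dose-DLT logistic regression on DLT-evaluable patients. Add, by dose level, the number stopped for drug-related toxicity that was not a DLT. State the 190 mg/m² MTD result with and without them, and say so if fewer than six evaluable patients remain there, since Section 5.1.2.1 requires at least six.
3. **Hematologic delays of more than 2 weeks (Section 6.1.5).** List them in the same tabulation only; they stay in the DLT denominator.
4. **Consistency.** The sponsor should reconcile Sections 5.2, 5.3.7, 6.1.6 and 6.4.1. No change to what counts as a DLT, or to when treatment stops, is proposed here.

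The cost is one phrase, one definition and one extra column. At closed dose levels only re-tabulation applies. Any later replacement for a dose decision would be occasional and should fit the accrual ceiling of 53, which is 6 above the planned maximum of 47 in Section 13.2.
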